4.1. Inclusion Criteria

Each potential subject must satisfy all of the following criteria to be enrolled in the study.

1. Subject requires hospitalization to treat influenza infection and/or to treat complications of influenza infection.
2. Subject tested positive for influenza A infection within 1 day of signing of the ICF using a PCR-based rapid molecular diagnostic assay.
3. Subjects must be capable of swallowing study medication tablets and capsules.
4. Subject must be male or female 18 to 85 years of age, inclusive.
5. Each subject (or their legally acceptable representative) must sign an ICF indicating that he or she understands the purpose of and procedures required for the study and is willing to participate in the study.
6. Subject must be willing and able to adhere to the prohibitions and restrictions specified in this protocol (see Section 4.3, Prohibitions and Restrictions).
7. Before randomization, a female subject must be either:
 - a. Not of childbearing potential:
 - i. postmenopausal (>45 years of age with amenorrhea for at least 12 months);
 - ii. permanently sterilized (eg, bilateral tubal occlusion [which includes tubal

ligation procedures as consistent with local regulations], hysterectomy, bilateral salpingectomy, bilateral oophorectomy);

iii. or otherwise incapable of pregnancy.

b. Of childbearing potential and

- i. practicing effective methods of birth control consistent with local regulations regarding the use of birth control methods for subjects participating in clinical studies
- ii. and agrees to continue using two methods of birth control throughout the study and for at least 90 days after receiving the last dose of study drug (see Section 4.3, Prohibitions and Restrictions)

8. A female subject of childbearing potential must have a negative urine pregnancy test at screening.
9. A female subject must agree not to donate eggs (ova, oocytes) for the purposes of assisted reproduction throughout the study and for at least 90 days after receiving the last dose of study drug (see Section 4.3, Prohibitions and Restrictions).
10. A male subject who is sexually active with a woman of childbearing potential and has not had a vasectomy must agree to use effective methods of birth control(see Section 4.3, Prohibitions and Restrictions), and all male subjects must also not donate sperm during the study and for 90 days after receiving the last dose of study drug.

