11.6. Efficacy Analyses

The efficacy endpoints will be analyzed on the Full Analysis Set, consisting of all subjects who were randomized, treated and had a confirmed influenza A infection, and will be analyzed by drug received.

Descriptive statistics will be used for all efficacy endpoints and will be tabulated by treatment arm and by age cohort. No formal statistical hypothesis testing will be made.

Clinical outcomes

The incidence of influenza complications will be categorized in a hierarchical fashion. The overall category will consist of any complication, consisting of the following subcategories:

- bacterial pneumonia (culture confirmed where possible),
- other bacterial superinfections,
- respiratory failure,
- pulmonary disease: asthma, chronic obstructive pulmonary disease [COPD]),
- cardiovascular and cerebrovascular disease (eg, myocardial infarction, congestive heart failure [CHF], arrhythmia, stroke),
- post-baseline ICU admission,
- all-cause mortality

The incidences on Day 28 of each (sub) category will be analyzed using logistic regression; baseline characteristics that are predictive of the incidence of complications can be included based on goodness of fit criteria. Odds ratios and associated 95% CIs will be reported of active vs. control treatment.

The time to improvement of vital signs is defined as the time from first study treatment to when at least 4 of 5 symptoms (temperature, blood oxygen saturation, heart rate, SBP, respiration rate) are recovered, including normalization of temperature and blood oxygen saturation. Normalization is defined in Table 6. If subjects satisfy these criteria at entry they will be censored at that time (effectively they will be excluded from the analysis). The data will be presented using a Kaplan-Meier curve. The time to event data will be modeled using the accelerated failure time (if the data provide an acceptable model fit) or alternatively a Cox proportional hazards model (in case the hazards are proportional). Additionally, the time to event data will be analyzed using the Gehan-Wilcoxon method.

Table 6: Resolution Criteria for Vital Signs

Assessment	Resolution Criterion
Temperature	≤ 37.2 °C or ≤ 37.8 °C rectal or tympanic
Oxygen saturation	$\geq 92\%$ on room air without supplemental oxygen
Respiration rate	≤ 24 /min
Heart rate	≤ 100 /min
Systolic blood pressure	≥ 90 mmHg

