Medical history will only be listed.

The influenza vaccination status will be tabulated by previous season, current season and both previous and current season (for subjects who got vaccinated in both seasons), overall and by age category, by treatment group (and overall).

The use of antiviral influenza medication prior to hospitalization will be tabulated separately, overall and by age category, by treatment group (and overall).

Influenza history will be listed, including information on first acute respiratory symptoms, influenza vaccination and previous antiviral influenza therapy. Pre-treatment Influenza complications will also be listed.

4.1.5. *Treatment Exposure and Compliance*

The treatment duration is defined as date/time of last study drug intake – date/time of first study drug intake + 12 hours.

Note: treatment interruptions will not be taken into account for the above definition.

Dosing compliance is calculated as the actual number of doses taken, as a percentage of the planned number of doses. The actual number of doses taken will be derived from the exposure information (EX domain) during hospitalization and from the drug accountability information (DA domain) after discharge from hospital.

In the exposure information the amount of medication administered during hospitalization is given per visit and time point, the actual number of tablets/capsules during hospitalization is the sum of this amount per medication for the records that are not outpatient records.

The actual amount of tablets/capsules taken after discharge will be derived from the drug accountability information as the difference between the drug dispensation at discharge and the returned amount (in case both amounts are known).

The actual number of doses taken during the study is the sum of the actual number of medication taken during hospitalization and after discharge, for Placebo or JNJ872 this number needs to be divided by 2 as the study uses 300 mg tablets. In total, the planned number of medication is 28 tablets of Placebo or JNJ872 and 14 capsules of Oseltamivir. Hence the planned number of doses per medication equals 14 doses.

Actual treatment duration and dosing compliance will be summarized descriptively overall and by age category, by treatment group (and overall).

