4.2.1. Clinical Outcomes

▪ **Incidence of influenza complications**

The incidence of influenza complications from first intake up to Day 28 will be categorized in a hierarchical fashion. The overall category will consist of any complication, consisting of the following subcategories

- bacterial pneumonia (culture confirmed where possible),
- other bacterial superinfections,
- respiratory failure,
- pulmonary disease: asthma, chronic obstructive pulmonary disease [COPD]),
- cardiovascular and cerebrovascular disease (eg, myocardial infarction, congestive heart failure [CHF], arrhythmia, stroke),
- post-baseline ICU admission,
- all-cause mortality

The occurrence (yes/no) of influenza complications from first intake up to Day 28 of each (sub) category will be analyzed using logistic regression with treatment group as covariate. In case influenza complications occur in both age categories, age category will also be added as a covariate and as an interaction with treatment group. If the model will not fit the age category and it's interaction will be removed. Odds ratios and associated 95% CIs will be reported of active vs. control treatment and – if available – of elderly patients vs. patients < 65 years.

▪ **Time to improvement of vital signs**

The time to improvement of vital signs is defined as the time (in hours) from first study treatment until the first assessment (actual date and time) of a successive series of 3 recordings (over 4 scheduled successive analysis time points, 1 missing time point is allowed) where at least 4 of 5 symptoms (temperature, blood oxygen saturation, heart rate, SBP, respiration rate) are recovered, with at least normalization of temperature and blood oxygen saturation. Normalization is defined in Table 6. If subjects satisfy these criteria at entry they will be censored at that time.

Only vital signs assessments assessed during hospitalization and up to Day 14 (during hospitalization) will be taken into account to determine time to improvement of vital signs. Assessments taken after hospital discharge or after day 14, whichever, comes first will not be taken into account. In case, there was more than one hospitalization period, only assessments of the first hospitalization period will be used.

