The time to return to usual activity and the time to return to usual health are defined as the time in hours from the first dose of investigational product till the first one of 2 successive cases where the response is 'Yes' on respectively FLU-PRO additional question 7 and FLU-PRO additional question 9. Missing data within the series are allowed as long as within three successive planned recordings there is at most 1 recording missing.

In cases where there are no sufficient recordings of return to usual activity/health as defined above, the endpoint will be censored. Censoring will be at the first time of return to usual activity/health, if and only if after this observation there is no recording of difficulties in usual activities/health (ignoring missing recordings). If there are no recordings of return to usual

activity/health satisfying this criterion, the time of censoring is the time of the last diary entry + 24 hours. One exception is censoring at the Day 28 Visit (last study day for the subject). If the subject is not returned to usual activity/health on this day, the time of the last diary entry will be taken as the time of censoring.

Data will be presented using Kaplan-Meier curves and Kaplan-Meier estimates by treatment group, overall and by age group. For a comparison between treatment arms, the time to parameters will be analyzed using an accelerated failure time model. The model will use the parametric shape, selected based on the goodness of fit criterion (AIC), and may take a Weibull, log-logistic, lognormal, or gamma distribution. As baseline covariates the ordinal scale at baseline category (ICU, ward+O₂, ward-O₂) and the age category (≥ 18 - < 65 years, ≥ 65 - ≤ 85 years) will be included. If the data don't provide an acceptable model fit, alternatively a Cox proportional hazards model can be used (in case the hazards are proportional). In case a Cox proportional hazards model is used a Log-log plot of survival will be added to check the proportional hazard assumption. Additionally, the time to event data will be analyzed using the logrank test and Gehan-Wilcoxon method.

- **Time to significant reduction in influenza symptom severity.**

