Data will be presented using Kaplan-Meier curves and Kaplan-Meier estimates. For a comparison between treatment arms, the time to hospital discharge in days will be analyzed using an accelerated failure time model. The model will use the parametric shape, selected based on the goodness of fit criterion (AIC), and may take a Weibull, log-logistic, lognormal, or gamma distribution. As baseline covariate the age category (≥ 18 - < 65 years, ≥ 65 - ≤ 85 years) will be included. If the data don't provide an acceptable model fit, alternatively a Cox proportional hazards model can be used (in case the hazards are proportional). In case a Cox proportional hazards model is used a Log-log plot of survival will be added to check the proportional hazard assumption. Additionally, the time to event data will be analyzed using the logrank test and the Gehan-Wilcoxon method.

4.3. **Safety**

All safety analyses will be done on the Safety Set. Analyses will be presented overall and by age category and by treatment group.

4.3.1. *Adverse events*

Pre-treatment AEs are defined as AEs that were reported or worsened after signing the ICF up to the start of study drug dosing. Treatment-emergent AEs (TEAE) are defined as AEs that were reported or worsened on or after the start of study drug dosing through the 28-day Safety Follow-up Visit.

Adverse events with a start date and time recorded will be allocated based on their start date and time. If there is no time recorded for the start of the adverse event the adverse event that occurred on or after the day of first treatment intake and not after the 28-day safety follow up visit will be considered as treatment-emergent. Only adverse events that occur before the day of first medication intake and after/on the day of signing ICF will be considered as pre-treatment.

In case the start date of an adverse event is partially or completely missing, a worst case allocation will be done using the available date and time information in the start and end date time of the adverse event (i.e. if possible based on the available information the adverse event will be allocated to the treatment phase and hospitalization sub period).

Adverse events

The variables related with adverse events are

- AE term (verbatim and MedDRA preferred term and system organ class)
- Onset date, End date and duration of AE
- Serious AE (Yes/No)
- Severity (Mild, Moderate, Severe, Life threatening)

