4.5. Health Care

The number of subjects admitted to the Intensive Care Unit (ICU) after baseline will be tabulated.

The length of ICU stay for subjects transferred to the ICU after baseline is calculated as:

$$\text{End date in ICU} - \text{Start date in ICU} + 1.$$

If a subject has multiple periods in the ICU the durations for these separate stays in the ICU will be summed.

Descriptive statistics of the duration in the ICU will be shown for all subjects that were admitted to the ICU after baseline.

References

Royal College of Physicians of London. (2012) National early warning score (NEWS): standardising the assessment of acute-illness severity in the NHS.. www.rcplondon.ac.uk/resources/national-earlywarning-score-news

Guideline, I. H. T. (2006). The clinical evaluation of QT/QTc interval prolongation and proarrhythmic potential for non-antiarrhythmic drugs E14. Recommended for adoption at Step, 4

White, I. R., Royston, P., & Wood, A. M. (2011). Multiple imputation using chained equations: issues and guidance for practice. *Statistics in medicine*, 30(4), 377-399.

World Health Organization. (2003) "WHO toxicity grading scale for determining the severity of adverse events."

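### The complication and ICU-admission incidences (SAP 4.2.1 and 4.5) are not restricted to subjects at risk: those already in the ICU, or with the complication, at first dose stay in the denominator, and the model has no baseline-status term.

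*SAP*

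**What the plan says.** Protocol 2.1 makes complications after the start of treatment a secondary objective. Entry does not require freedom from them. The first inclusion criterion reads "Subject requires hospitalization to treat influenza infection and/or to treat complications of influenza infection", and none of the exclusion criteria in Protocol 4.2 bars ICU patients. SAP 4.2.6 expects some, since its covariate list begins "As baseline covariates the ordinal scale at baseline category (ICU" and continues with two ward categories.

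SAP 4.2.1 defines the analysis: "The occurrence (yes/no) of influenza complications from first intake up to Day 28 of each (sub) category will be analyzed using logistic regression". The subcategories include post-baseline ICU admission and all-cause mortality. SAP 4.2 puts all efficacy analyses on the Full Analysis Set, and SAP 3.2 sets no condition on baseline complications or ICU status for that set. The model contains treatment and, if complications occur in both age categories, age and its interaction with treatment. The age terms are removed if the model does not fit.

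For baseline complications, SAP 4.1.4 says only "Pre-treatment Influenza complications will also be listed". SAP 4.5 adds "The number of subjects admitted to the Intensive Care Unit (ICU) after baseline will be tabulated", without an at-risk denominator. On covariates, Protocol 11.6 is wider than the SAP: "baseline characteristics that are predictive of the incidence of complications can be included based on goodness of fit criteria".

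**The concern.** An incidence describes subjects who could have the event. Someone already in the ICU at first dose cannot be admitted to it without leaving first, so that subject stays in the denominator as a non-event whatever the treatment does. The same can happen in a complication subcategory when the condition was present at entry and does not worsen. SAP 4.2.1 does not say how a complication ongoing at first dose is scored.

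The SAP deals with baseline status elsewhere in the same section. Subjects who already meet the vital-signs criterion at entry are censored at that time, which Protocol 11.6 says effectively excludes them. The Day 8 ordinal model adjusts for the baseline category. The complication model does neither.

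At stake are the reported incidences and risk differences, and the reader's ability to tell a treatment difference from a difference in who was in the ICU or already had a complication at entry.

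**Working it through.** **The plan's own figures.** The documents give none for complications. The nearest is the risk difference for 4/60 versus 1/30 adverse events, stated as 3.3% (-19%, 26%) in SAP Table 4. An exact unconditional interval, ordered on the raw difference, gives -19.0% to 25.5%, so it reproduces. For a zero difference at 60:30 the table gives ±22 points, which is used below as a yardstick.

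**Inputs.** Allocation is 2:1 with up to 90 subjects, so 60:30, or 40:20 if 60 enrol (SAP 1.4, 1.5). Event risks and the share not at risk, f, are not in the documents and are assumed.

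**1. Dilution, same f in both arms.** Counted risk = (1 - f) × risk among those at risk.

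| Assumed risk at risk, active vs control | f | Counted risks | Risk difference (points) | Odds ratio |
|---|---|---|---|---|
| 10% vs 20% | 0 | 10% vs 20% | -10 | 0.444 |
| 10% vs 20% | 10% | 9% vs 18% | -9 | 0.451 |
| 10% vs 20% | 20% | 8% vs 16% | -8 | 0.457 |
| 10% vs 20% | 30% | 7% vs 14% | -7 | 0.462 |
| 5% vs 10% | 30% | 3.5% vs 7% | -3.5 (from -5) | 0.482 (from 0.474) |
| 15% vs 30% | 30% | 10.5% vs 21% | -10.5 (from -15) | 0.441 (from 0.412) |

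Example for f = 30%: (0.07/0.93) / (0.14/0.86) = 0.0753/0.1628 = 0.462. Incidence and risk difference shrink by the factor 1 - f; the odds ratio hardly moves. Restricting to subjects at risk restores -10 points and 0.444.

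**2. How often the arms differ at baseline.** SD of the difference in f = sqrt(f(1 - f)(1/60 + 1/30)).
- f = 20%: sqrt(0.16 × 0.05) = 0.089, about 9 points.
- f = 30%: sqrt(0.21 × 0.05) = 0.102, about 10 points.
- Binomial probability of a difference of at least 10 points, for f = 10%, 20%, 30%: 17%, 31%, 37% at 60:30; 28%, 42%, 49% at 40:20.

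**3. What an imbalance does with no drug effect.** Assume a risk of 20% among those at risk in both arms.
- f = 10% active, 20% control: 18% vs 16%, a difference of +2 points, odds ratio 1.15 (0.87 with the shares reversed).
- f = 10% active, 30% control: 18% vs 14%, a difference of +4 points, odds ratio 1.35 (0.74 reversed). A 20-point imbalance is about 2.2 SD at f = 20% (20/8.9), so this case is uncommon.

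**The case against.** The strongest reply is that the treatment comparison barely changes. With balanced arms the odds ratio goes from 0.444 to 0.462. A 10-point chance imbalance moves the risk difference by 2 points against an interval of about ±22 points, and that interval already allows for chance imbalance. This stands, and it limits the point to dilution and noise. It does not rescue the incidences, which the interval does not correct.

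Several other replies also stand:
- Under SAP 4.3.1 a baseline complication that worsens after dosing can count as an event, so subjects with an entry complication are not all scored no.
- A subject in the ICU remains at risk of death and of other complications, so the ICU problem concerns one subcategory.
- Entry requires swallowing tablets and capsules (Protocol 4.1), which limits how many of the sickest ICU patients can enter.
- Baseline NEW Score, oxygen saturation, respiration rate and supplemental oxygen are already summarised by arm (SAP 4.1.2).
- The narrower SAP model does not contradict the protocol, which only permits further covariates. A small model is defensible for sparse events.

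A reader might also infer that admission complications are widely miscounted as on-treatment events, because SAP 4.3.1 treats as treatment-emergent an untimed event described as "the adverse event that occurred on or after the day of first treatment intake and not after the 28-day safety follow up visit". The documents do not support that. Adverse events are collected only from consent (Protocol 12.1.1), so a complication that predates consent and does not worsen is outside the rule. It can misplace only a complication that starts between consent and first dose, on the date of first intake, with no recorded time. No share is given for these, so no size can be attached. For records other than adverse events, SAP 3.1.1 sets a missing start time to 0:00, which points the other way.

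**Conclusion.** The concern holds as a matter of denominators and baseline adjustment. With 10% to 30% of subjects not at risk, reported incidences and risk differences are 10% to 30% too small relative to those among subjects at risk. The odds ratio is nearly unaffected when the arms are balanced. Baseline differences of 10 points or more are quite likely at these sample sizes, and the model has no term for them. All shares and event risks here are assumptions.

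A reader might conclude that the analysis favours one arm because the sickest subjects count as ICU non-events. Randomisation does not support that reading: the scoring applies to both arms, and imbalance can fall either way. The analysis is secondary and without formal testing, and the primary pharmacokinetic endpoint is untouched. The change is worth making because it is cheap and makes the incidences interpretable.

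**What to change.** In SAP 4.2.1, 4.5 and 4.1:
1. Analyse and tabulate post-baseline ICU admission in subjects not in the ICU at first dose. Analyse each other complication subcategory in subjects free of it at first dose, where the pre-treatment complication record carries the category; SAP 4.1.4 does not show that it does, so this needs checking. Print the number at risk by arm. Keep all subjects for death. State how a complication ongoing at first dose is scored.
2. For any complication, keep the full set and add the baseline ordinal category (or ICU or complication at baseline, yes/no) as a covariate, under the existing rule that terms are dropped if the model does not fit. Take baseline status before the first dose, because SAP 4.2.1 assigns the worst category of each day and a Day 1 value could include a transfer after dosing.
3. Tabulate baseline ICU status and pre-treatment complications by arm instead of only listing the latter.

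The cost is SAP wording, slightly smaller denominators and one more term in a sparse model. The baseline ordinal category is already used in SAP 4.2.1 and 4.2.6, so no new data are needed for the ICU part.

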1.4. Sample Size Justification

Up to 90 subjects in total will be enrolled in this study. An effort will be made to include at least 24 subjects for each cohort, with the total of subjects allowed to be recruited across both cohorts. It is anticipated that it is feasible to recruit at least 60 subjects, which would lead to an acceptable precision for the primary objective.

For the primary objective of evaluating the PK of JNJ-63623872 across age cohorts the PK parameters considered of major importance are C_{min} , C_{max} , and AUC_{12h} . As there are no data available where Day 3 has been part of extensive PK sampling on the 600 mg bid dose, the variability on days with available data are presented in Table 1. Based on those data a between-subjects CV of 60% was assumed as a reasonably conservative estimate for the current study.

Table 1: Variability for Key Pharmacokinetic Parameters for JNJ-63623872 600 mg bid (Between-subjects %CV)

Time point	N	C_{min}	C_{max}	AUC_{12h}
Day 1	12	NA	65	56
Day 5	18	77	57	61
Day 5*	18	48	57	46
Day 10	12	56	44	43

Note: Based on study 63623872FLZ1001.

*JNJ-63623872 600 mg bid + oseltamivir 75 mg bid.

NA: Not applicable.

For age cohorts it was assumed that the number of hospitalizations would be about equal for elderly and non-elderly adults. In case 60 subjects are enrolled, there are 40 subjects on active treatment and it is assumed that at least 16 subjects are on active treatment in each cohort). For the comparison of PK parameters of the cohort of elderly adults (test) vs. non-elderly adults (reference) with PK data in a 16 to 24 ratio and a between-subject coefficient of variation (CV) of 60%, the 90% confidence interval (CI) of the geometric mean ratio (GMR) for C_{min} would be predicted to have a half-width of 35%, indicating that we can be 90% confident that the true GMR is in the interval observed GMR/1.35 to 1.35*GMR. If 90 subjects were enrolled with 60 on active treatment in a 24 to 36 ratio, the predicted half-width would be 28%.

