1.5. Randomization and Blinding

Central randomization will be implemented in this study. Subjects will be randomly assigned to 1 of 2 treatment arms in a 2:1 ratio (active vs. placebo) based on a computer-generated randomization schedule prepared before the study by or under the supervision of the sponsor. The randomization will be balanced by using randomly permuted blocks and will be stratified by age cohort. An interactive web response system (IWRS) will assign a unique treatment code, which will dictate the treatment assignment and matching study drug kit for the subject. The requestor must use his or her own user identification and personal identification number when contacting the IWRS, and will then give the relevant subject details to uniquely identify the subject.

The investigator will not be provided with randomization codes. The codes will be maintained within the IWRS, which has the functionality to allow the investigator to break the blind for an individual subject.

Data that may potentially unblind the treatment assignment (ie, study drug plasma concentrations) will be handled with special care to ensure that the integrity of the blind is maintained and the potential for bias is minimized. This can include making special provisions, such as segregating the data in question from view by the investigators, clinical team, or others as appropriate until the time of database lock and unblinding.

Under normal circumstances, the blind should not be broken until all subjects have completed the study and the database is finalized. Otherwise, the blind should be broken only if specific emergency treatment/course of action would be dictated by knowing the treatment status of the subject. In such cases, the investigator may in an emergency determine the identity of the treatment by contacting the IWRS. It is recommended that the investigator contact the sponsor or its designee if possible to discuss the particular situation, before breaking the blind. Telephone contact with the sponsor or its designee will be available 24 hours per day, 7 days per week. In the event the blind is broken, the sponsor must be informed as soon as possible. The date, time, and reason for the unblinding must be documented by the IWRS, in the appropriate section of the electronic case report form (eCRF), and in the source documents. The documentation received from the IWRS indicating the code break must be retained with the subject's source documents in a secure manner.

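### The complications logistic model can enter a treatment-by-age interaction on two events, names no contrast for the active-vs-control odds ratio, and has a fallback that drops the stratification factor without a stated criterion

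*SAP*

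**What the plan says.** SAP 4.2.1 (Clinical Outcomes) models the occurrence of complications up to Day 28 for an overall category and seven subcategories, among them respiratory failure, post-baseline ICU admission and death. The starting model has treatment only. If complications occur in both age categories, "age category will also be added as a covariate and as an interaction with treatment group". If that model does not fit, age and its interaction are both removed. The output is specified as "Odds ratios and associated 95% CIs will be reported of active vs. control treatment", plus an elderly-vs-younger odds ratio where available.

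On size, SAP 1.4 states "Up to 90 subjects in total will be enrolled in this study" and "It is anticipated that it is feasible to recruit at least 60 subjects". On the age split, "An effort will be made to include at least 24 subjects for each cohort", and "it was assumed that the number of hospitalizations would be about equal for elderly and non-elderly adults". SAP 1.5 gives 2:1 allocation and says that randomisation "will be stratified by age cohort".

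Three other places bear on the point. SAP 3.4 asks for displays by age stratum and overall, without a rule for combining strata. SAP 4.2.2 uses the same kind of interaction for viral AUC and does name its contrasts: overall and by age category. Protocol 11.6 allows predictive baseline covariates in the complications model and mentions no interaction.

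**The concern.** There are three linked gaps.

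- **Undefined odds ratio.** With the interaction in the model there is no single treatment odds ratio. Under reference coding, the treatment coefficient is the effect in whichever age group is the reference. Under effect coding it is the equal-weight average of the two log odds ratios. The SAP does not choose.
- **Weak trigger.** One event in each age group adds the interaction, but two events cannot fill four treatment-by-age cells. With an empty cell, the maximum-likelihood estimate for this model is not finite.
- **Unclear fallback.** Failure to fit is not defined. When the fallback acts, it goes straight to treatment only and skips the model with treatment and age as main effects, so the randomisation stratum is lost.

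The result could be a table of eight odds ratios that come from different models, mean different things, and in sparse rows carry no information.

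**Working it through.** **Inputs.** From SAP 1.4 and 1.5: 90 subjects (60:30) or 60 subjects (40:20), with about equal cohorts. The four cells are then 30, 15, 30, 15 or 20, 10, 20, 10 (active, control within each age group). The complication rate *p* is in neither document, so I assume a common rate of 5% to 30%.

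**The plan's own figures.** None exists for this model. The nearest figure with the same arm size is the zero-event upper limit for 60 treated subjects, 1 − 0.05^(1/60) = 4.9%, which matches SAP Table 3.

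**Chance of an empty cell once the interaction is triggered.** Write *q* = 1 − *p*, and let *a* and *c* be the active and control cell sizes in each age group.

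- P(all four cells have an event) = (1 − q^a)² (1 − q^c)²
- P(trigger) = (1 − q^(a+c))²
- P(empty cell | trigger) = 1 − the ratio of the first to the second

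Example with 90 subjects and p = 10%: 0.9^30 = 0.0424, 0.9^15 = 0.2059 and 0.9^45 = 0.0087. The first term is 0.9576² × 0.7941² = 0.578 and the second is 0.9913² = 0.983. The result is 1 − 0.578/0.983 = 41%.

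**Chance that a main-effects model fails.** Given the trigger, the model with treatment and age has no finite treatment odds ratio only if a whole arm has no events. That probability is [(1 − q^a)² q^(2c) + (1 − q^c)² q^(2a)] / P(trigger). The treatment-only fallback fails in the same cases.

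| Assumed rate | Interaction, N=90 | Main effects, N=90 | Interaction, N=60 | Main effects, N=60 |
|---|---|---|---|---|
| 5% | 78% | 18% | 89% | 27% |
| 10% | 41% | 4% | 64% | 11% |
| 20% | 7% | 0.1% | 22% | 1% |
| 30% | 1% | <0.1% | 6% | 0.1% |

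A 66/24 age split with 90 subjects raises the interaction-model figure to 55% at a 10% rate and 19% at 20%.

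**Which odds ratio?** Take hypothetical counts of 3/30 active and 3/15 control under 65, and 8/30 and 3/15 at 65 or over.

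- Under 65: (3/27)/(3/12) = 0.44 (95% CI 0.08 to 2.53)
- 65 or over: (8/22)/(3/12) = 1.45 (0.32 to 6.53)
- Equal-weight average: √(0.44 × 1.45) = 0.80 (0.25 to 2.54)
- Main-effects model: 0.90 (0.29 to 2.75)

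The first three come from one fitted interaction model, and each could be labelled active vs control.

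**Does an empty cell announce itself?** I fitted the interaction model to 3/30, 0/15 (under 65) and 3/30, 2/15 (65 or over) with a general binomial GLM routine, not the SAS version the SAP names. It reported convergence, with a treatment log odds ratio of 20.4 and a standard error of about 12,444. The main-effects model on the same counts gives 1.56 (0.29 to 8.27).

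**The case against.** The strongest reply is that the fallback already deals with sparse data. A reader might infer from the empty-cell figures that the reported odds ratio will often be inestimable, or that most subcategory rows will be unusable. The documents do not support that. The figures describe the first-step model. If the fallback is applied, the treatment-only model fails no more often than the main-effects model, and an absurd estimate can fairly be read as a model that did not fit. What remains is that nobody has written down that reading, and that acting on it discards age when dropping the interaction alone would do.

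Sparse data is also an assumption. At 20% to 30% with 90 subjects, the empty-cell risk is only 7% to 1%, and the overall category could lie there.

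A reader might also infer that the interaction itself costs precision. It need not. With 90 subjects at 10%, one stratum's log odds ratio has variance 1/3 + 1/27 + 1/1.5 + 1/13.5 = 1.11 (SE 1.05). The average of the two strata has SE √(1.11/2) = 0.75, the same as for a common effect. The loss comes from reporting a single stratum.

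Finally, SAP 3.4 and 4.2 already call for summaries by stratum and overall, and raw counts will be shown. That limits the harm, but neither section defines the overall odds ratio.

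**Conclusion.** The point holds as a specification defect in a secondary analysis. The missing contrast applies at any event rate whenever the interaction stays in the model, and SAP 4.2.2 shows that the authors know how to name one. The sparse-cell problem depends on the assumed rate. At rates of about 10% or below, the interaction model has an empty cell in 41% or more of triggered cases with 90 subjects and 64% or more with 60; by 30% the risk is 1% and 6%. These figures assume equal cohorts and one common rate across arms and age groups. The fallback has no criterion and removes the stratification factor, so rows may not be comparable. The study tests no formal hypothesis and its primary objective is pharmacokinetic, so no error rate or decision rule depends on this table.

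**What to change.** For the overall category and every subcategory, take the active-vs-control odds ratio and 95% CI from one logistic model with treatment and age category as main effects. Use Firth penalised likelihood, or an exact method, when cells are sparse. Define sparse in advance by a count, for example any treatment-by-age cell without an event, or use Firth in every row so that the method does not change. Show age-specific results as counts and percentages. Any stratum-specific odds ratio should be labelled descriptive, with no interaction test, because SAP 4.2 rules out formal testing. Delete the undefined fallback.

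The cost is a few sentences in the SAP and a small code change. The table would no longer contain a modelled interaction estimate. That is a small loss, since at these sample sizes the estimate would be very imprecise for the rarer categories.
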